### **6.3.3 Guardian 4 Transmitter**

The Guardian 4 Transmitter is a portable, electrical current meter intended to process, store, and transmit glucose sensor values to the compatible insulin pump. The transmitter sends SG values and sensor integrity (SI) data from the sensor to compatible insulin pumps via a Bluetooth Low Energy wireless communication protocol.

D00409632 Version E Page 39 of 106

## 6.4 Non-Investigational Product(s)

### 6.4.1 Insulin

Lyumjev (insulin lispro-aabc injection) is a fast-acting insulin with the same active ingredient as Humalog, used to treat children and adults with diabetes for the control of high blood sugar. Lyumjev is an approved insulin for administration via continuous subcutaneous insulin infusion (CSII) in children and adults.

Subjects will use rapid-acting analogue insulin (Novolog, Humalog or Admelog) during the run-in period. During the study period, subjects will be provided with Lyumjev for use.

#### **6.4.2 Medtronic Extended Infusion Set**

Infusion sets are single-use by patients with diabetes mellitus requiring subcutaneous administered insulin to maintain acceptable BG levels. The Medtronic Extended infusion set is an infusion set with a pre-loaded inserter, inserted into the subcutaneous tissue of a user, and is connected to a Medtronic MiniMed Extended Reservoir (for use with a Medtronic MiniMed insulin pump). There are three basic components of the infusion set:

- 1. Catheter hub with cannula and adhesive patch
- 2. Tubing
- 3. Tubing connector

The cannula, connected to the catheter hub, is introduced into subcutaneous tissue (i.e., infusion site). The tubing connects the catheter hub and the tubing connector to provide the fluid from the medication reservoir housed within the insulin pump.

The device utilizes a new high-performance tubing connector (H-Cap) to replace the current proprietary Paradigm connector (P-Cap), an extended wear tubing to replace the current tubing, and an extended wear adhesive patch. Figure 2 and Figure 3 illustrates the device and the tubing connectors. The Medtronic Extended infusion set enhances patient wear time to 7 days. This is done by maintaining insulin formulation stability (including physical, chemical, and microbiological stability) during infusion through the pump/infusion set system over extended time (up to 7 days).

D00409632 Version E Page 40 of 106

Figure 2. Medtronic Extended infusion set

[figure not shown]

Figure 3. Connector, P-Cap (Left); High-Performance Connector, H-Cap (Right)

D00409632 Version E Page 41 of 106

### 6.4.3 Medtronic Extended Reservoir

The Medtronic Extended Reservoir is indicated for the subcutaneous infusion of insulin from compatible Medtronic insulin pumps and Medtronic Extended infusion sets.

#### **6.4.4 One-Press Serter**

The One-Press Serter, referred to as the Serter in this protocol, is an insertion device that is used to ensure correct placement of the sensor into the user's subcutaneous tissue. Insertion is triggered when the two spring loaded buttons on the sides of the Serter are pressed simultaneously. The Serter is intended as a single patient, non-sterile, multi-use device.

## 6.4.5 Charger

The Charger is used to recharge the transmitter as needed. A fully charged battery provides up to 7 days of transmitter use. The system includes a battery charger that will recharge the device according to the user quide.

#### 6.4.6 Tester

The Tester operates as a sensor simulator creating signal current at a level that is within the range of an in-vivo sensor during normal operation.

### **6.4.7 CareLink Personal Software**

Medtronic CareLink Personal software is an internet-based software system which allows the device data to be uploaded and reviewed by the subject. The CareLink Personal software allows subjects to upload data from Medtronic MiniMed insulin pumps and a range of system-supported, third-party BG meters. The data contained in CareLink Personal software is accessible to users using a standard browser, i.e., Microsoft® Internet Explorer or Google Chrome, on an Internet enabled personal computer (PC).

The CareLink Personal software uses standard Transport Layer Security (TLS) technology. TLS transmission protocol invokes encryption on both ends of the transmissions and is the standard for all security-based systems. The encryption remains in effect whether the data is moving to and from the client and server in the United States, or to and from a client in another country to the United States. The data is secure behind a three-tier industry standard architecture, which places the database behind three different firewalls, where each firewall separates a tier:

- The internet to the web server;
- Web server to the application server;
- Application server to the database server.

### **6.4.8 CareLink System Software**

Medtronic CareLink system software is an internet-based software system, which allows the device data to be uploaded, viewed and easily evaluated by the physician. The CareLink system software allows retrospective review of device data and was developed for use by the investigational center staff. The CareLink system software allows the investigational center staff to manage, create, and request for approval to link the subject's account. The data contained in CareLink system software is accessible to users using a standard browser, i.e., Microsoft® Internet Explorer or Google Chrome, on an Internet enabled PC.

The CareLink system software use standard TLS technology. TLS transmission protocol invokes encryption on both ends of the transmissions and is the standard for all security-based systems. The encryption remains in effect whether the data is moving to and from the client and server in the United States, or to and from a client in another country to the United States. The data is secure behind a three-

D00409632 Version E Page 42 of 106

tier industry standard architecture, which places the database behind three different firewalls, where each firewall separates a tier:

- The internet to the web server:
- Web server to the application server;
- Application server to the database server.

## 6.4.9 FoodPrint App by Nutrino

The FoodPrint app by Nutrino is a meal logging app. FoodPrint can also be used to log workouts, sleep, medications, blood glucose, and insulin.

#### 6.4.10 Roche Accu-Chek Guide Glucose Meter

The Roche's Accu-Chek Guide Link meter is a home BG meter designed to measure and transmit BG values to the compatible insulin pumps via a Bluetooth Low Energy wireless communication protocol. The insulin pump then sends the BG values to the transmitter. The transmission of BG values from a compatible meter is an optional feature provided as a convenience to the user; it eliminates the need to manually enter BG values into the pump. The Accu-Chek Guide Link BG meter is compatible with Roche's Accu-Chek Guide test strips.

## 6.4.11 Accessory Applications – MiniMed 780G system

The MiniMed Clinical app is an optional accessory, which receives pump data via Bluetooth Low Energy wireless communication from the pump. The MiniMed Clinical app provides users with the convenience to wirelessly transfer pump data to CareLink Personal/CareLink system software and also provides a mirroring display of the pump screen. The MiniMed Clinical app is not designed to control or monitor the performance of the insulin pump nor for direct monitoring of pump data. As a mirroring display, the app can provide alerts to the subject via the user interface. All alerts must be addressed on the insulin pump.

The CareLink Clinical app is an optional accessory which receives pump data wirelessly from the CareLink server. The CareLink Clinical app provides a mirroring display of the MiniMed Clinical app screen, for remote monitoring by a care partner (e.g., caregiver). The CareLink Clinical app is not designed to monitor the performance of the insulin pump nor for direct monitoring of pump data. As a mirroring display, the app can provide notifications to the care partner via the user interface.

### 6.4.12 Blue Adapter

The Blue Adapter is an optional accessory with Bluetooth technology that facilitates the communication between a PC and the insulin pump, via a Bluetooth Low Energy wireless communication protocol. The Blue Adapter is an off-the-shelf non-medical device intended to transfer data to CareLink server. The Blue Adapter does not have any computation, diagnostic, monitoring or therapeutic function/benefit. Medtronic will provide the Blue Adapter as a convenience to subjects as an alternative for subjects when automatic uploads via the MiniMed Clinical app are not possible.

#### 6.4.13 Ketone Meter

The ketone meter can measure both BG (sugar) and blood β-Ketone. In this study, however, the meter will only be used to measure ß-Ketone levels, which will be collected for reporting and review (see Investigator/Coordinator binder for details) and as described in the body of this study protocol. This meter allows quantification of blood β-Ketone levels and is the preferred patient method of testing over urine testing.

D00409632 Version E Page 43 of 106

### 6.4.14 Smartphone

Sponsor may provide a smartphone, upon request.

### 6.5 Consumable Devices

Glucose meter accessories and other consumable materials will be provided to subjects for use in the study.

## 6.6 Anticipated Product Changes

There are no changes anticipated for any of the products/devices during the course of the study.

## **6.7 Product Accountability**

Good clinical research practice requires that investigators and research teams ensure accurate accountability for any investigational devices used in a research trial. It is expected that all investigational devices will be used in the manner intended during the study and that they will be used only by (on) subjects who have consented to participate in the research study and by investigational center staff trained on the study.

Any investigational device and insulin being used in clinical research must be strictly accounted for and will not be shipped to any investigational center unless all of the necessary approvals (e.g., regulatory authority and IRB) have been received.

The principal investigator (PI) or an authorized designee shall keep records documenting the receipt, use, return, and disposal of the investigational devices and insulin. Additional details regarding product accountability and product disposition requirements are provided in **Table 2**.

D00409632 Version E Page 44 of 106

## **Table 2. Product Accountability Requirements**

Device/Drug	Record on Site Received eCRF	Record Disbursement, Returned or Not Returned from Subject on Subject Device Identification	Subject Return Device to Investigational Center	Record Returned or Not Returned to Sponsor on Site Returned eCRF	Investigational Center Return Device to Sponsor at Conclusion of Study
M: 14 1 7000		eCRF			•
MiniMed 780G Insulin Pump (MMT-1884)	Yes	Yes	Yes	Yes	Yes
Guardian 4 Sensor (MMT- 7040)	Yes	Yes	Yes (Unused and used with complaint) No (Used)	Yes	Yes (Unused and used with complaint) No (Used)
Guardian 4 Transmitter (MMT-7841)	Yes	Yes	Yes	Yes	Yes
Medtronic Extended Infusion Set (MMT-430, MMT- 431, MMT-432, MMT-433, MMT- 440, MMT-441, MMT-442 and MMT-443)	No	No	Yes (Complaint) No* (Used)	No	Yes (Complaint) No* (Used)
Medtronic Extended Reservoir (MMT- 342)	Yes	Yes	Yes (Complaint) No* (Used)	Yes	Yes (Complaint) No* (Used)
Roche Accu-Chek Guide Link Study Meter (08116083022)	Yes	Yes	Yes	Yes	No*
Ketone Meter	No	No	Yes	No	No*
Lyumjev insulin	Yes	Yes	Yes (Unopened vials)	Yes	No**
Smartphone, as approved for distribution	Yes	Yes	Yes	Yes	Yes

\*If subject is unable to dispose, return products to investigational center for disposal. If investigational center is unable to dispose, return products to sponsor for disposal.

\*\*Insulin leftovers should be destroyed at investigational center

D00409632 Version E Page 45 of 106

The investigational center will promptly notify the sponsor of any device and insulin handling violation that might impact either the safety and/ or welfare of subjects or data integrity.

### 6.7.1 Receipt and Inventory of Study Devices/Insulin by Investigational Center

- Upon receipt of the study product, investigational center staff will take inventory of the shipment, making sure that information on the packing slips/invoices matches exactly the contents of the containers, as applicable, including:
  - Ship to address
  - o Reference number
  - Device type
  - Quantity
  - Quantity per package
  - Lot number (where applicable)
  - Serial number (where applicable)
- Ensure that devices, insulin, and supplies received have not reached or exceeded their expiration
- Sign and date the packing slips/invoices, noting any discrepancies, and file in appropriate study binder
- Notify the study monitor of any discrepancies

Enter or acknowledge the study device and insulin information on the appropriate eCRF in the study database, if applicable as described in Table 2.

## 6.7.2 Storage of Study Devices/Insulin at Investigational Center

Study devices and insulin are to be stored in a secure environment with access limited to authorized research personnel. Study devices and insulin are stored in the appropriate environmental conditions as identified in the IFU/user guide/labeling.

### 6.7.3 Dispensing of Study Devices/Insulin

Each time a study device and insulin is dispensed to a subject by the investigator or authorized member of the research team, eCRF, and/or source documentation will be completed as required. Documentation may include:

- Dispensing date
- Subject identification (ID)
- Lot number (where applicable)
- Serial number (where applicable)
- Device type
- Amount dispensed

## 6.7.4 Return or Disposal of Study Devices/Insulin

After use by the subject, the investigational center is expected to accept and retain all devices and insulin as described in **Table 2** and store them in a secure environment. If containers/units/devices are missing, the reasons should be documented in the applicable eCRF and/or source document. If discrepancies between the amounts used by subjects and the amounts expected to be returned exist, the reasons should be documented in the applicable eCRF and/or source document.

Requirements for return of devices and insulin by subjects to the investigational center and return of device and insulin by the investigational center to the sponsor are listed in Table 2. The devices and insulin that are being returned to the investigational center may be returned to the sponsor as subjects complete the study, at the study closure or upon sponsor request.

D00409632 Version E Page 46 of 106

Other consumable devices (e.g., alcohol wipes, study meter supplies, and tape), and accessories shipped in kits, supplies or materials may be returned to the sponsor, they may be retained by investigational centers for educational purposes only, or they may be disposed of appropriately by the investigational center staff.

Disposable and consumable devices that have been **used** by a subject will be disposed of appropriately by the subject or the investigational center staff during the conduct of the study.

All study devices and insulin that are required to be entered into the study database and/or source document must be accounted for as described above before they are returned to the sponsor.

Lyumjev insulin will be accounted for at the investigational center. Any insulin that is left over will be destroyed by participating centers and destruction records will be filed.

# 7. Study Site Requirements

## 7.1 Investigator/Investigational Center Selection

In order to conduct the study, it is required that the investigator and investigational center staff have the appropriate medical training. The principal investigator must be a physician who has managed patients on both CGM and insulin pump therapy for at least one year and must be familiar with insulin carbohydrate ratios, insulin sensitivity, and treating diabetic emergencies.

# 7.2 Study Site Activation

During the activation process (prior to subject enrollment), Medtronic will train investigational center staff who may then train other staff at each investigational center. If new members join the study investigational center team, they will receive training on the applicable study requirements relevant to their role before contributing to the study.

Prior to performing study related activities, all regulatory requirements shall be fulfilled, including but not limited to the following:

- IRB approval (and voting list, as required by local law) of the current version of the Clinical Investigation Plan (CIP) and Informed Consent Form (ICF), and report of prior investigations
- Regulatory authority approval or notification (as required per local law)
- Fully executed Clinical Trial Agreement (CTA)
- Financial disclosure (if applicable)
- Curriculum vitae (CV) of investigators
- Documentation of delegated tasks
- Documentation of study training

In addition, all participating investigational center staff must be trained on the current version of the CIP as well as on the applicable study requirements depending on their role and must be delegated by the PI prior to performing delegated study activities.

Medtronic will provide each study investigational center with documentation of study investigational center/investigator subject enrollment readiness; this letter must be received prior to subject enrollment.

D00409632 Version E Page 47 of 106

# 8. Selection of Subjects

## 8.1 Study Population

A total of up to 250 subjects with insulin-requiring type 1 diabetes age 7-80 will be enrolled at up to 25 investigational centers across the United States in order to have at least 200 subjects enter the study period. Up to 125 subjects will be enrolled in the pediatric age group (7-17 years of age) and up to 125 in the adult age group (18 years or older):

Subject Age Group	Sub-groups	Enrollment Goal (N)			
Dodiatric	All Pediatric	Minimum 100 Subjects			
Pediatric Age 7 – 17 years	Age 7 - 13 years	Minimum 20 Subjects			
7.gc 7 = 27 years	Age 14 - 17 years	Minimum 20 Subjects			
Adult Age 18 - 80 years	N/A	Minimum 100 Subjects			

A minimum of 10 subjects and a maximum of 40 subjects is targeted for enrollment at each investigational center to ensure that the results from the individual investigational center may be pooled for analysis.

Investigational centers will be encouraged to enroll a study population that represents a wide variety of backgrounds.

# **8.2 Subject Enrollment**

Subjects will be considered enrolled in the study upon signing the ICF and assent form (if applicable). A subject will be assigned a unique study subject ID via the eCRF, which is a 9-digit code (335XXXXXX). The first three digits refer to the CIP number (335), the next three digits refer to the investigational center number, and the last 3 digits refer to the subject number assigned during Visit 1 (e.g., 335002001 is subject 001 from investigational center 002).

The investigator will maintain a log of all subjects enrolled in the clinical study, assigning a subject ID linked to their names, and alternative subject ID.

#### 8.3 Inclusion Criteria

- 1. Age 7-80 years at time of screening.
- 2. Has a clinical diagnosis of type 1 diabetes:
  - a. 14–80 years of age: A clinical diagnosis of type 1 diabetes for 2 years or more as determined via medical record or source documentation by an individual qualified to make a medical
  - b. 7–13 years of age: A clinical diagnosis of type 1 diabetes for 1 year or more as determined via medical record or source documentation by an individual qualified to make a medical diagnosis.
- 3. Does not require a legally authorized representative to consent on their behalf due to mental or intellectual disability.
- 4. Subject or parent/caregiver is literate and able to read the language offered in the pump or pump materials.

D00409632 Version E Page 48 of 106

- 5. Subject and/or legally authorized representative is willing to provide informed consent for participation.
- 6. Is willing to perform fingerstick blood glucose measurements as needed.
- 7. Is willing to wear the system continuously throughout the study.
- 8. Must have a minimum daily insulin requirement (Total Daily Dose) of greater than or equal to 8 units and a maximum total daily dose of 250 units or less.
- 9. Has a Glycosylated hemoglobin (HbA1c) less than 10% (as processed by Central Lab) at time of screening visit.

Note: All HbA1c blood specimens will be sent to and tested by a National Glycohemoglobin Standardization Program (NGSP) certified Central Laboratory. HbA1c testing must follow NGSP standards.

- 10. Has thyroid-stimulating hormone (TSH) in the normal range OR if the TSH is out of normal reference range, the Free T3 is below or within the lab's reference range and Free T4 is within the normal reference range.
- 11. Uses pump therapy for greater than 6 months (with or without CGM experience) prior to screening
- 12. Is willing to upload data from the study pump, must have Internet access, and a computer system, or compatible smartphone that meets the requirements for uploading the study pump.
- 13. Is willing to take one of the following insulins and can financially support the use of either of the 2 insulin preparations as required during the run-in period:
  - a. Humalog (insulin lispro injection)
  - b. NovoLog (insulin aspart injection)
  - c. Admelog (insulin lispro injection)
- 14. Is willing to take Lyumjev insulin during the study period (supplied via Sponsor).

#### 8.4 Exclusion Criteria

- 1. Has a hypersensitivity to insulin lispro or one of the excipients in Lyumjev
- 2. Has a history of 2 or more episodes of severe hypoglycemia, which resulted in any the following during the 6 months prior to screening:
  - a. Medical assistance (i.e., Paramedics, Emergency Room [ER] or Hospitalization)
  - b. Coma
  - c. Seizures
- 3. Has been hospitalized or has visited the ER in the 6 months prior to screening resulting in a primary diagnosis of uncontrolled diabetes.
- 4. Has had DKA in the last 6 months prior to screening visit.
- 5. Will not tolerate tape adhesive in the area of sensor placement as assessed by a qualified individual.
- 6. Has any unresolved adverse skin condition in the area of sensor placement (e.g., psoriasis, dermatitis herpetiformis, rash, Staphylococcus infection).
- 7. Is female of child-bearing potential and result of pregnancy test is positive at screening.
- 8. Is sexually active female of child-bearing potential and is not using a form of contraception deemed reliable by the investigator.
- 9. Is female and plans to become pregnant during the course of the study.
- 10. Is being treated for hyperthyroidism at time of screening.
- 11. Has diagnosis of adrenal insufficiency.
- 12. Has taken any oral, injectable, or intravenous (IV) glucocorticoids within 8 weeks from time of screening visit, or plans to take any oral, injectable, or IV glucocorticoids during the course of the study.
- 13. Is using hydroxyurea at time of screening or plans to use it during the study.
- 14. Is actively participating in an investigational study (drug or device) wherein he/she has received treatment from an investigational study drug or investigational study device in the last 2 weeks.

D00409632 Version E Page 49 of 106 Medtronic

- 15. Is currently abusing illicit drugs.
- 16. Is currently abusing marijuana.
- 17. Is currently abusing prescription drugs.
- 18. Is currently abusing alcohol.
- 19. Is using pramlintide (Symlin), DPP-4 inhibitor, liraglutide (Victoza or other GLP-1 agonists), metformin, canagliflozin (Invokana or other SGLT2 inhibitors) at time of screening.
- 20. Has a history of visual impairment which would not allow subject to participate in the study and perform all study procedures safely, as determined by the investigator.
- 21. Has elective surgery planned that requires general anesthesia during the course of the study.
- 22. Has sickle cell disease, hemoglobinopathy; or has received red blood cell transfusion or erythropoietin within 3 months prior to time of screening.
- 23. Plans to receive red blood cell transfusion or erythropoietin over the course of study participation.
- 24. Is diagnosed with current eating disorder such as anorexia or bulimia.
- 25. Has been diagnosed with chronic kidney disease that results in chronic anemia.
- 26. Has a hematocrit that is below the normal reference range of lab used.
- 27. Is on dialysis.
- 28. Has serum creatinine of >2 mg/dL.
- 29. Has celiac disease that is not adequately treated as determined by the investigator.
- 30. Has had any of the following cardiovascular events within 1 year of screening: myocardial infarction, unstable angina, coronary artery bypass surgery, coronary artery stenting, transient ischemic attack, cerebrovascular accident, angina, congestive heart failure, or ventricular rhythm disturbances.
- 31. Has had history of cardiovascular event 1 year or more from the time of screening without
  - a. a normal EKG and stress test within 6 months prior to screening or during screening or
  - b. clearance from a qualified physician prior to receiving the study devices if there is an abnormal EKG or stress test.
- 32. Has 3 or more cardiovascular risk factors listed below without a normal EKG within 6 months prior to screening or during screening or clearance from a qualified physician if there is an abnormal EKG:
  - Age >35 years
  - Type 1 diabetes of >15 years' duration
  - Presence of any additional risk factor for coronary artery disease
  - Presence of microvascular disease (proliferative retinopathy or nephropathy, including microalbuminuria)
  - Presence of peripheral vascular disease
  - Presence of autonomic neuropathy
- 33. Is a member of the research staff involved with the study.
- 34. Has used a MiniMed 780G pump prior to screening

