# 9.7 Deviation Handling

A deviation is any instance(s) of failure to follow, intentionally or unintentionally, the requirements of the CIP. It is expected that the investigator will conduct this clinical trial in compliance with the CIP and all applicable regulations governing the conduct of clinical research involving human subjects. Failure to do so could result in one or all of the following:

- Investigational center disqualification
- · Notification to the regulatory authorities/IRB depending on the severity of the deviation and reporting requirements

The investigator should not implement any deviation from, or changes to, the CIP without agreement by the sponsor and prior review and documented approval/favorable opinion from the regulatory authority (if applicable) or IRB, except where necessary to eliminate an immediate hazard(s) to subjects. The use of waivers from the CIP are prohibited in this study.

Subjects 21 years of age and older are asked for an HbA1c test at Visit 1, Visit 7, Visit 12, Visit 14 and Visit 15. Failing to take the test at Visits 1 and 15 will result in a deviation. Failing to take the test at visits 7, 12 and 14 will not be subject to a deviation.

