- During the study, the subject experiences one severe hypoglycemic episode, if it is related to the use of 780G system SmartGuard feature.
- During the study, the subject experiences one episode of DKA, if it is related to the use of 780G system SmartGuard feature.
- During the study, subject has a cardiovascular event or any vascular event such as stroke.
- During the course of the study, subject has ≥2 infusion site reactions that meet criteria for adverse event reporting.

Documentation of the reason(s) leading to subject withdrawal will be kept in the subject's source documentation.

D00409632 Version E Page 73 of 106

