**Insulin infusion site reaction:** any reaction at the site of insulin infusion assessed as moderate or severe should be reported as an AE.

- A moderate insulin infusion site reaction is defined as follows:
  - o Pain: If pain interferes with daily activities or requires treatment
  - Erythema: If the erythema is 51-100mm in diameter, bright red or dark with ulceration or necrosis at the infusion site
  - o Pruritis: If pruritis causes frequent itching and occasionally impairs daily activities
- A severe insulin infusion site reaction is defined as follows:
  - Pain: If pain limits daily activities and requires treatment
  - Erythema: If the Erythema is >100mm in diameter, bright red or dark with ulceration or necrosis at the infusion site.
  - o Pruritis: If pruritis causes near constant itching and severely impairs daily activities

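### Exclusion criteria 5 and 6 screen skin and adhesive problems only at the sensor area, not at the infusion-set area, where two adverse-event-level reactions of any cause mandate withdrawal

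*Protocol*

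**What the plan says.** **Eligibility.** Protocol 8.4 has two exclusions about skin. Criterion 5: "Will not tolerate tape adhesive in the area of sensor placement as assessed by a qualified individual". Criterion 6: "Has any unresolved adverse skin condition in the area of sensor placement", with psoriasis, dermatitis herpetiformis, rash and Staphylococcus infection as examples. The synopsis carries the same limit. The nearest criterion concerned with the infused product is number 1, "Has a hypersensitivity to insulin lispro or one of the excipients in Lyumjev", which is about the drug and not the skin.

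**Exposure.** Protocol 6.4.2: "The Medtronic Extended infusion set enhances patient wear time to 7 days". The same section describes an adhesive patch made for extended wear. All subjects use this set in both the run-in and the study period.

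**Handling of reactions.** Protocol 11.2 makes "any reaction at the site of insulin infusion assessed as moderate or severe" an adverse event. Protocol 9.8 lists among the grounds on which a subject will be withdrawn that the "subject has ≥2 infusion site reactions that meet criteria for adverse event reporting". Neither passage is qualified by cause or by a pre-existing condition.

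**The concern.** The protocol recognises the skin hazard at both body interfaces but screens for it at only one. A subject with active dermatitis or a skin infection confined to the infusion-set area, or who does not tolerate the set's patch there, meets every entry criterion.

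Two things are at stake. The first is subject protection: a patch designed for a week's wear may be used in an area with a problem that, in the sensor area, would have barred entry. The second is interpretation. The study is meant to support labelling of a new insulin-device pairing and has no control arm. A site reaction in such a subject could come from the skin condition, the adhesive, the set or Lyumjev, and the design gives little means of telling which. Two such reactions also remove the subject.

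**Working it through.** The point rests on the text. The arithmetic serves only to size the consequence.

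**1. Coverage of the criteria.** All 34 exclusions in 8.4 were read against the question of whether they would stop a subject with a skin or adhesive problem limited to the infusion-set area. Criteria 5 and 6 would not, because both name the sensor area. Criterion 1 would not, because it is limited to insulin lispro and the Lyumjev excipients. No exclusion is a general investigator-judgement clause. Inclusion 11 (more than 6 months of pump use) rules out neither a current skin condition nor intolerance of this extended-wear patch. The documents do not say whether sensor and infusion areas overlap on the body; where they do, criteria 5 and 6 already apply.

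**2. The same hazard elsewhere in the protocol.**

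| Item | Sensor | Infusion set |
|---|---|---|
| Skin risks listed (10.1) | Irritation, rash, infection and others | Irritation, rash, localized infection and others |
| Entry criterion (8.4) | Yes, numbers 5 and 6 | None |
| Specific withdrawal count (9.8) | None | Two or more adverse-event-grade reactions |

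**3. Attribution.** Table 3 marks the question about infusion reactions with Lyumjev, and its dedicated assessment form, from Visit 8 on. The run-in has general adverse-event questions but not this item, so there is no like-for-like baseline on the subject's own insulin. Sections 11.3 and 11.6 classify causality to device or procedure, with no insulin category.

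**4. How readily the withdrawal rule is met.** The documents give no reaction rate, so the per-wear risk p is an assumption. With independent weekly wears, 90/7 is about 13 wears in the study period, and

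P(two or more) = 1 − (1−p)^13 − 13p(1−p)^12.

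- p = 1%: 0.7%
- p = 2%: 2.7%
- p = 5%: 1 − 0.513 − 0.351 = 13.5%
- p = 10%: 1 − 0.254 − 0.367 = 37.9%

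The rule therefore bears mainly on subjects with a persistently raised risk, the kind a skin criterion would screen for.

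**5. Effect on power.** Inputs for the adult time-in-range superiority test (Protocol 14.5.1, SAP 6.2.1): assumed mean 76% against 73.7%, a difference of 2.3; SD 7.2; one-sided 0.025; one-sample t-test. Power is the probability that a noncentral t with n−1 degrees of freedom and noncentrality (2.3/7.2)√n exceeds its critical value.

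- The plan's own case, n = 80: 80.6%, in line with the stated figure of more than 80%.
- The planned cohort, a minimum of 100 per age group and 200 entering the study period: n = 100 gives 88.6%.
- After losing 1, 3 or 5 of 100 (an assumed range): 88.2%, 87.6% or 86.9%.
- Primary endpoints at n = 95 in adults: HbA1c (margin 0.4, SD 0.7) 99.98%; time in range with the 7.5-point margin, about 100%.

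**6. What a withdrawal costs in data.** Effectiveness uses Visit 13 to end of study (SAP 7.9.3), and CGM endpoints are not imputed (SAP 7.4). A subject withdrawn before Visit 13 gives no time-in-range data; one withdrawn later still contributes. HbA1c is collected on early exit after Visit 7 (Protocol 9.5.4) and is otherwise multiply imputed.

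**The case against.** The strongest reply is that the set is a non-investigational product (Table 1) whose risks are dealt with in its labelling, so limiting study-specific skin exclusions to the investigational sensor is a coherent choice. There are also working safeguards. By the visit windows, subjects wear the same set for about 11 to 24 days on their own insulin before Lyumjev starts (Visit 6 at day 11 to 17, Visit 7 up to 7 days later), so patch intolerance can surface first. Someone withdrawn in run-in never enters the ITT set. Section 9.8 tells the investigator to withdraw a subject whose health would be compromised, with skin-site infection and severe adhesive reaction as examples. Section 10.1 has an irritated set moved, and nothing requires placing it on diseased skin.

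Much of this stands and lowers the weight of the point. But apart from prior pump use, the safeguards act mostly after the set has been worn, and run-in reactions themselves count towards the two. Labelling not reproduced here cannot stand in for an entry criterion.

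Three stronger inferences are tempting and are not supported:

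- **That such reactions count against Lyumjev.** Sites do ask about reactions with Lyumjev, but formal causality is to device or procedure, and an underlying illness is a ground for calling an event not related. Site reactions are neither a tested endpoint nor a named item in the safety summaries (SAP 7.9.6, 7.10). Attribution is confounded, not assigned to the drug.
- **That the losses push power below 80%.** That takes losses from a cohort of 100 and subtracts them from 80, the number the power statement requires. It also concerns a secondary test that plays no part in pass/fail (SAP 7.9.1).
- **That the waiver clause forces enrolment.** Section 9.7 says "The use of waivers from the CIP are prohibited in this study"; this bars departures from the plan and does not oblige an investigator to enrol everyone who qualifies.

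**Conclusion.** The gap holds. Criteria 5 and 6 stop at the sensor area, no other criterion covers the infusion-set area, and the adverse-event and withdrawal provisions for infusion sites ignore cause. The consequence is a modest weakness in subject protection and in the interpretability of site reactions, within a single-arm study. It is not a threat to the tested endpoints: adult time-in-range superiority power moves by 1.7 points (88.6 − 86.9) if 5 of 100 are lost, and the primary tests are essentially unaffected.

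The number of affected subjects is unknown, since the documents give neither a prevalence nor a reaction rate. The loss of 1 to 5 per 100 and the per-wear risks of 1% to 10% are illustrations only. The conclusion about eligibility depends on neither.

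**What to change.** Reconcile criteria 5 and 6 with the infusion-site risk, adverse-event and withdrawal passages by extending their scope, in Protocol 8.4 and the synopsis, to *in the area of sensor or infusion set placement*. This point asks for no change to the withdrawal rule or to the analysis.

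The cost is a short protocol amendment, a slightly wider skin check at a screening visit that already has to assess the sensor area, and possibly a few more screen failures. No new visit or test is needed.
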